In the event that a patient is unable to achieve adequate calories parenterally, and is unable to tolerate enteral feeds, it may be necessary to evaluate whether or not the patient should continue the therapy with Omegaven® as monotherapy or resume therapy with conventional fat emulsions so that additional parenteral fat calories can be given. The clinical team, in conjunction with the patient's primary physician, will determine if the patient should be removed from the protocol.

In-patient administration:

Orders for Omegaven® will contain the following data elements: body weight, total daily dose (ml), and hourly infusion rate (ml/hour). Prior to the administration of each Omegaven® dose, two nurses will check the dose dispensed against the physician's orders and verify that the

infusion pump settings (hourly rate, volume to be infused) are correct before the infusion is started.

As previously mentioned, Omegaven® may be infused in the same manner as conventional fat emulsions through either a central or peripheral line. The emulsion is isotonic. It is compatible with parenteral nutrition solutions and may be co-infused with TPN via y-site. The product may be infused through a 1.2 micron inline filter.

Outpatient Monitoring and Administration for patients on home therapy

After the initial evaluation by the Division of Neonatology, patients will return to the clinic for routine follow-up. Subjects will be asked to return to the clinic every 2 weeks for the first 2 months of treatment. Thereafter, patients will return to the clinic on a monthly basis, or as directed by the Division faculty. It will be explained to the parent/legal guardian that these follow up visits are important and that the study physicians reserve the right to drop the subject for non-compliance if safety measures cannot be adequately monitored.

Orders for home use of Omegaven® will be signed by the Division of Neonatology physicians, ensuring that subjects are compliant with study parameters while receiving the treatment drug. Orders for the Omegaven® will include: body weight measurement, total daily dose (ml), and hourly infusion rate (ml/hr). Prior to each Omegaven® dose, the nurse and/or parent will check the dose dispensed against the physician's orders and verify that the infusion pump settings (hourly rate, volume to be infused) are correct before the infusion is started.

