Adverse events (AEs) and serious adverse events (SAEs) will be assessed and reported from the time of the first Omegaven® infusion until Omegaven completion and resolution of event(s). This is a very high risk population so adverse events are not uncommon. However, events such as death, blood stream infection, the development or worsening of respiratory distress, or hemodynamic instability; electrolyte abnormalities, catheter malfunction, bowel obstruction, and urinary tract infection will be reported. Any serious or unexpected adverse events will be reported to the SIUH IRB within 48 hours, and the FDA within 7 days. In particular, the patient will be observed during and shortly after Omegaven® administration for the occurrence of anaphylactic or allergic reactions. As inpatients, those experiencing adverse events that are moderate or severe in nature and that may be related to Omegaven® will have their treatment temporarily halted until the adverse event has resolved. Dose modifications will occur as described above. Patients receiving Omegaven® at home will be observed by their parent or caregiver. If adverse events that are moderate or severe in nature as an outpatient, parents will be told to report to the Emergency Department at Staten Island University Hospital for evaluation and possible hospital admission for their child. If a dose reduction is made for adverse events later considered to be unrelated to Omegaven®, the Omegaven® dose will be increased back to the dose prescribed prior to the dose reduction. Patients with anaphylactic or allergic reactions will not continue treatment.

Adverse events and serious adverse events will be collected and reviewed monthly for emerging patterns.

Patients will be withdrawn from Omegaven® treatment for any of the following:

- a) Parent/legal guardian requests to discontinue treatment and/or observation for any reason.
- b) A suitable organ has been located and the patient is able to undergo a liver or liver/intestinal transplant.
- c) Decision by the Principal Investigator that termination is in the patient's best medical interest.
- d) Omegaven will be stopped if lipid intolerance persists despite therapeutic changes as described on page 3 of the protocol (see Dose Modification).
- e) Omegaven will be stopped if essential fatty acid levels are below normal two serial measurements.

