The infusion of Omegaven® can lead to a prolonged bleeding time and an inhibited platelet aggregation. In rare cases, patients may experience a fishy taste. The administration of Omegaven® should be stopped or reduced if there is a marked increased in blood glucose levels during the Omegaven® infusion. Undesirable effects that are seen during the infusion of Omegaven® that may also occur with conventional fat emulsions (i.e., Intralipid®) include slight rise in body temperature, flushing or cyanosis, vomiting, changes in blood pressure, erythema, anaphylactic reactions.

Overdose:

In the event of an overdose of Omegaven® there is a risk of developing fat overload syndrome that may occur when the triglyceride level rises >200 mg/dL acutely as a result of too rapid a rate of infusion, or chronically at high infusion rates in associated with a change in the patient's clinical condition (e.g., renal dysfunction, sepsis). In such cases, the infusion should be stopped or, if necessary, continued at a reduced dose. Metabolic acidosis has occurred in patients receiving Omegaven® at excessive doses without simultaneous administration of dextrose.

Potential Benefit of Omegaven® Treatment

Omegaven® may be effective in stabilizing or reversing hepatic injury associated with the use of parenteral nutrition. It may allow the patient to continue to receive the majority of his/her caloric intake from parenteral nutrition while advancing on enteral nutrition or awaiting liver or liver/intestinal transplant.

Outcome Variables

Laboratory measurements, growth indices and trends will be reviewed as per the suggested monitoring schedule during Omegaven therapy. Desired endpoint to support effectiveness will be evidenced by a decline in serum direct bilirubin levels below 2 on two serial measures.

Potential Risks of No Treatment

Since Omegaven® will only be offered to those patients for whom no standard therapy is likely to be safe and effective, the risks of not being treated are those allowing for the natural history of their disease and associated clinical manifestations to progress. These include fulminate liver failure and death.

Data Safety and Monitoring Plan

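### Outcome review is tied to the time on Omegaven, so children whose therapy ends before the bilirubin endpoint may leave with unknown outcome

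*Protocol*

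**What the plan says.** Under Outcome Variables the Protocol states: "Laboratory measurements, growth indices and trends will be reviewed as per the suggested monitoring schedule during Omegaven therapy". The endpoint meant to support effectiveness is "a decline in serum direct bilirubin levels below 2 on two serial measures". No time point or denominator is attached to it.

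Several routes can end therapy before that endpoint is met:

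- **Nutritional failure.** Under Details of Omegaven® Administration, a child who is "unable to achieve adequate calories parenterally, and is unable to tolerate enteral feeds" is evaluated on whether to "continue the therapy with Omegaven® as monotherapy or resume therapy with conventional fat emulsions so that additional parenteral fat calories can be given". Those treating the child, together with the primary physician, "will determine if the patient should be removed from the protocol". No criterion for that decision is stated.
- **Non-compliance.** The outpatient monitoring section lets the study physicians drop a child whose safety cannot be adequately monitored.
- **Withdrawal list.** Adverse Event Criteria and Reporting Procedures includes, as item (b), "A suitable organ has been located and the patient is able to undergo a liver or liver/intestinal transplant" and, as item (c), a decision by the investigator in the child's interest. Item (a), parental request, distinguishes stopping treatment from stopping observation.

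The same section follows adverse events until Omegaven is completed and the events have resolved. The outpatient section rules out blood tests taken purely for the study.

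**The concern.** The Protocol's hypothesis is that giving Omegaven instead of soybean emulsion prevents or reverses cholestasis, and it names an endpoint to support effectiveness. To judge that, one needs to know what became of every child who started. A review window that closes when Omegaven stops loses the later course of children who stop early.

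Early stopping is unlikely to be random. Failure to feed by either route and progression to transplant are plausibly related to the course of the liver disease, while the children who stay on include those advancing on feeds until weaned from PN. The Protocol's own case for Omegaven, under Preliminary Studies, cites fewer deaths and transplantations than in historical controls. Yet transplant ends treatment, and with it the stated review window.

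At stake is whether a favourable result among children still on therapy reflects the treatment or the selection of who stayed.

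**Working it through.** The Protocol states no sample size, response rate or removal rate, so there is no figure to reproduce. The check has two parts.

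**1. The text side by side.**

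| Question | Where | Answer |
|---|---|---|
| When are outcomes reviewed? | Outcome Variables | While on Omegaven |
| Can therapy end before the endpoint? | Details of Omegaven® Administration; outpatient monitoring; withdrawal list | Yes, by several routes |
| Is there a rule for keeping or removing a child after nutritional failure? | Details of Omegaven® Administration | Case-by-case judgement |
| Is bilirubin followed after stopping? | Tables 2 and 3 | Both are schedules for Omegaven therapy. Table 2 runs until bilirubin has cleared but lists only the fatty acid profile and coagulation tests. Bilirubin is in Table 3. |
| Are adverse events followed after stopping? | Adverse Event Criteria and Reporting Procedures | To resolution of the event, which is not efficacy follow-up |

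No section schedules bilirubin, transplant or survival as outcomes once Omegaven has stopped.

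**2. Possible size, with assumed counts.** Take 20 starters, of whom 10 reach the endpoint on therapy and m are removed first. Let k of those m recover later.

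- Proportion among those remaining: 10/(20 − m)
- Proportion among all starters: (10 + k)/20

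With k = 0:

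- m = 2: 10/18 − 10/20 = 55.6% − 50.0% = 5.6 points
- m = 5: 10/15 − 10/20 = 66.7% − 50.0% = 16.7 points
- m = 8: 10/12 − 10/20 = 83.3% − 50.0% = 33.3 points

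The direction depends on k. For m = 5, the all-starter proportion runs from 10/20 = 50% (k = 0) to 15/20 = 75% (k = 5), against 66.7% among those remaining. The on-therapy figure is too high for k = 0 to 3 (at k = 3, 13/20 = 65%) and too low for k = 4 or 5 (at k = 4, 14/20 = 70%). Without follow-up k is unknown, so the result is uncertain by m/20: 10, 25 or 40 points for m = 2, 5 or 8.

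A second set of assumptions gives a similar order of size. Let r be the share of starters who recover on Omegaven and m now the share removed, none of whom recovers. The proportion among those remaining is r/(1 − m):

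| r | m = 10% | m = 20% | m = 30% |
|---|---|---|---|
| 50% | 55.6% | 62.5% | 71.4% |
| 60% | 66.7% | 75.0% | 85.7% |

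The excess over r runs from 5.6 to 25.7 points.

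**The case against.** The strongest reply is that this is a compassionate-use protocol with a desired endpoint for each child and no stated response rate. Who is counted, and how removal or transplant is classified, commonly belongs in a statistical analysis plan, which is not shown. That stands: the absence of a denominator is not an error here. But an analysis plan cannot recover outcomes that the Protocol does not arrange to record, and the recording window is set in the Protocol.

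A second reply is that Outcome Variables does not say review happens solely during therapy, and that other sections point to some later information. Item (a) of the withdrawal list separates treatment from observation, death is a reportable event, surgical procedures and readmissions are recorded for outpatients, and Patient Confidentiality mentions autopsy reports for deaths close in time to the study. This narrows the gap. Some transplants and deaths would be known, and a transplant withdrawal is at least a named reason. It does not supply later bilirubin, or systematic transplant and survival follow-up after removal.

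Third, the Protocol gives no prognosis data. The trigger for discretionary removal is nutritional, not a bilirubin level, and a drop for non-compliance has no evident link to liver outcome. That also stands. The link is plausible for nutritional failure and transplant, but it is not shown.

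A reader might also infer that a child who goes back to conventional lipid could be counted as an Omegaven responder. The text does not support this. It requires a child to stay on the Protocol receiving both emulsions. The contrast between monotherapy and extra parenteral fat calories permits that reading without settling it, and a child switched completely would fall outside the review window instead.

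**Conclusion.** The concern holds as a gap in outcome recording. Review is stated for the period on Omegaven, therapy can end before the endpoint for reasons plausibly related to prognosis, and no section provides for efficacy outcomes afterwards. An effectiveness judgement based on children still on therapy could therefore be too favourable.

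The size cannot be derived from the document. The range of about 6 to 33 points assumes 20 starters, 10 recoveries, 2 to 8 removals and no recovery among those removed. If enough of the removed children recovered later, the bias would shrink or reverse.

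A reader might go further and conclude that the Protocol adopts a biased response rate, or that the removed children are those least likely to recover. Neither follows: no rate is defined, and no prognosis figures are given.

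**What to change.** In Outcome Variables, extend the review so that, for every child given a first infusion, the following continue to be recorded from the chart after Omegaven stops or the child is removed, unless the parent withdraws from observation:

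- direct bilirubin from routine care
- lipid received
- PN status
- transplant
- survival

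State that results will be reported for all children who started. Those who, before the endpoint, were removed, switched to or also given conventional lipid, transplanted, or died should appear as separate categories and not be omitted. Separate categories are preferable to scoring every such child as not reversed. That scoring answers a different question from whether starting Omegaven reverses the liver disease, and it could understate benefit, for example in a child dropped for non-compliance whose bilirubin later clears.

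The cost is a few sentences of Protocol text, some added chart review and possibly a lower reported response. No study blood draws are needed, which respects the Protocol's limit to routine tests. The clinical decisions on lipid choice and removal are unchanged.

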Lipid Intolerance. If lipid intolerance develops (defined as serum triglyceride levels > 200 mg/dl), the following will be considered prior to reducing the dose: a) if the level was obtained while the patient was receiving a continuous 24 hour infusion of Omegaven®, the total dose should be infused over 20 hours, and a repeat serum triglyceride level obtained prior to resuming the infusion 4 hours later, b) other sources of lipid intolerance should be considered and addressed (drugs, renal disease). If the triglycerides continue to remain high despite the aforementioned interventions, a dosage reduction of 25% of the current dose will be considered. If subsequent triglyceride levels are elevated the dosage will continue to be reduced, and then Omegaven will be discontinued if there is no effect of dose reduction. Subsequent levels will be monitored and adjustments made. After a week, if triglyceride levels are in an appropriate range, Omegaven will be reintroduced.

Duration of Therapy. Patients will remain on Omegaven® until weaned from PN. Patients may continue monotherapy with Omegaven® as an additional source of calories after the dextrose/protein portion of PN is discontinued. Omegaven may be restarted within seven days of discontinuing therapy. After seven days, and meeting inclusion criteria, Omegaven can resume at the initial dose of 0.5 grams/kg/day, advancing to 1 gm/kg/day

Adverse Event Criteria and Reporting Procedures

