Appendix Materials

Table 1

Comparison of Parenteral Fat Emulsions

	Intralipid® 20%	Liposyn® II 20%	Omegaven® 10%
Soybean oil	100%	50%	
Safflower oil		50%	
Fish oil			100%

% of Total Fat:

Linoleic acid	50	65	0.1 – 0.7
α-Linolenic acid	9	4	0.2
EPA			1.25 - 2.82
DHA			1.44 - 3.09
Arachidonic acid			0.1 - 0.4
Glycerol	2.3	2.5	2.5
Egg Phospholipid	1.2	1.2	1.2
Total kcals per ml	2.0	2.0	1.12
Available in the U. S.	Yes	Yes	No

Table 2: Schedule for Required Safety Monitoring for Omegaven® Therapy

(To be done baseline pre-Omegaven® therapy and serially as indicated until direct bilirubin <2.0 mg/dL on two serial measurements)

Parameter	Baseline	Every 2 wk to every month
Essential Fatty Acid Profile	X	X (month)
PT	X	X
PTT	X	X
INR	X	X

Table 3: **Suggested** Monitoring Schedule for Omegaven® Therapy

Parameter	Baseline (pre-therapy)	Daily	Every 2 wk to monthly
Body Weight	X	X	
Length; head circumference	X		X
Fluid intake	X	X	
Laboratory tests:			
Sodium, Potassium	X		X
Chloride, Bicarb.	X		X
Glucose	X		X
BUN/Creatinine	X		X
Triglycerides	X		X
Ca, P, Mg	X		X
Albumin	X		X
ALT (SGPT)/AST	X		X
Alk phosphatase	X		X
Fractionated Bilirubin	X		X
GGT	X		X
Cholesterol	X		X
Hemoglobin/Hct	X		X
WBC	X		X
Platelets	X		X
PT	X		X
PTT	X		X
INR	X		X

***For safety purposes:** serum triglycerides, coagulation labs are obtained at baseline, then biweekly for 4 weeks, and monthly thereafter; fatty acid profile is obtained at baseline, then monthly thereafter. Dose reduction will occur if there is evidence of lipid intolerance (serum triglycerides > 200mg/dL) or evidence of bleeding. Growth indices include weight, length, and head circumference will be computed every 2 weeks. Infants receiving Omegaven for more than one month will have vitamin E and copper levels drawn.

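### A dose cut for bleeding is to be reversed once the bleed is judged unrelated, even if bleeding continues, which conflicts with the protocol's own bleeding rule

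*Protocol*

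**What the plan says.** All references are to the Protocol.

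- **Reversal** (Adverse Event Criteria and Reporting Procedures). Where the dose was cut because of an event "later considered to be unrelated to Omegaven®, the Omegaven® dose will be increased back to the dose prescribed prior to the dose reduction".
- **Halt** (same section). Inpatients with moderate or severe events "that may be related to Omegaven® will have their treatment temporarily halted until the adverse event has resolved".
- **Outpatients** (same section). For moderate or severe events, "parents will be told to report to the Emergency Department" for evaluation and possible admission.
- **Cross-reference** (same section). "Dose modifications will occur as described above". The Dose Modification section above it gives dose steps for raised triglycerides only.
- **Bleeding** (Appendix Materials, footnote to Table 3). "Dose reduction will occur if there is evidence of lipid intolerance (serum triglycerides > 200mg/dL) or evidence of bleeding". No grade of bleeding and no size of reduction is given.
- **Drug effect** (Risks and Discomforts; Side effects). Both sections say the drug can lengthen bleeding time and inhibit platelet aggregation. Risks and Discomforts lists severe hemorrhagic disorders and hemodynamic instability among the contraindications.
- **Entry** (Patient Selection and Inclusion/Exclusion Criteria). Active coagulopathy, shown by continuing bleeding or a need for clotting factors, is an exclusion. So is hemodynamic instability.

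**The concern.** The reversal rule treats causality as the whole question. For many events that is reasonable: if the drug did not cause the problem, there is little reason to keep an infant on less lipid. Bleeding differs, because a drug that impairs platelet function can worsen a bleed that began for another reason, such as surgery or sepsis. Judging the bleed unrelated does not make a higher dose safe while it continues.

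At stake is what a clinician does for a very high-risk child, aged from birth to 5 years, who is still bleeding after the event has been classed as unrelated. The written instructions point both ways, and the one in the main text raises the dose.

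**Working it through.** No arithmetic applies. The protocol gives no size for the bleeding reduction, so the re-increase cannot be computed. What is known is the ceiling: under Details of Omegaven® Administration the dose starts at 0.5 g/kg/day and rises to a maximum of 1 g/kg/day.

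**Step 1. Which rule governs each kind of ongoing bleed?**

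| Ongoing bleed | Halt rule | Table 3 footnote | Reversal rule | Result |
|---|---|---|---|---|
| Inpatient, moderate or severe, possibly related | Halt until resolved | Reduce | Does not apply | Workable: the halt is the stricter rule |
| Inpatient, mild, possibly related | Does not apply | Reduce | Does not apply | Consistent |
| Inpatient, dose cut, then judged unrelated | Does not apply | Reduce | Increase back | Conflict |
| Outpatient, dose cut, then judged unrelated | Does not apply | Reduce | Increase back | Conflict |

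The reversal sentence does not name bleeding. The last two rows rest on reading a cut made for bleeding as a dose reduction for an adverse event, which is the natural reading.

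**Step 2. Can the halt rule's recovery condition be carried over?** No. It is limited to inpatients and to events that may be related, and an event judged unrelated is outside it by definition. A halt already in place is arguably untouched, since the reversal sentence speaks of reductions and not of halts. A bleed judged unrelated from the outset never triggers the halt.

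**Step 3. Does the cross-reference resolve it?** No. It leads to Dose Modification, which has no bleeding step. The bleeding rule stands only in the footnote to a table headed as a suggested schedule.

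**Step 4. Does the protocol use recovery as a test elsewhere?** Yes. The halt lasts until the event resolves. After a stop for lipid intolerance, "After a week, if triglyceride levels are in an appropriate range, Omegaven will be reintroduced". The reversal sentence has no comparable condition.

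**Step 5. Do the general safeguards close the gap?** Investigators may lower the dose at their discretion (Details of Omegaven® Administration). Withdrawal item (c) covers a "Decision by the Principal Investigator that termination" is in the child's best interest. The contraindications can be read as applying throughout treatment, in which case they cover severe hemorrhagic disorders, though not every bleed. These allow a clinician to depart from the reversal sentence. They do not change what it says.

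**The case against.** The best defence is that the footnote carries no causality condition. While bleeding persists it still calls for a reduction, so the protocol read as a whole does not simply send a bleeding child back to full dose. That stands, and it is why the finding is a conflict between two rules. A reader might infer that the protocol compels the full dose during any bleed; the text does not support that.

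The severity threshold in the halt rule also gives a sensible ladder for possibly related inpatient bleeds: halt the worse ones, reduce for the rest. Since the protocol names bleeding effects of the drug, many significant bleeds would count as possibly related. This narrows the gap to bleeds judged unrelated and to outpatients, for whom the protocol text states no hold.

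Three further inferences are tempting and should not be drawn:

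- *That caregivers have no written instruction about the infusion on the way to the Emergency Department.* The protocol text is silent, but it provides for parental training and home nursing, and those materials are not shown.
- *That the restart rule readmits excluded children.* "Omegaven may be restarted within seven days of discontinuing therapy", and after seven days on meeting the inclusion criteria; both sentences permit and do not require. Hemodynamic instability is already a contraindication, the infection exclusion is tied to initiation, and a restart at the initial dose is plausibly an initiation. Naming the exclusions there is a clarification only.
- *That every unrelated event should resolve before the dose goes back up.* Reportable events include urinary tract infection and catheter malfunction. Waiting for each could prolong low lipid intake in children who may not tolerate enteral fat, and low essential fatty acid levels on two serial measurements are themselves a reason to stop treatment.

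**Conclusion.** The point holds in a narrow form. For an ongoing bleed judged unrelated, the reversal sentence and the Table 3 footnote give opposite instructions. The halt rule and the Dose Modification section do not decide between them, and discretion and the contraindications only soften the conflict.

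This is a patient-safety wording defect that should be corrected. It affects no statistical figure. How often the situation would arise cannot be estimated from the protocol. The conclusion assumes that a reduction for bleeding counts as a reduction for an adverse event, and that no document outside the protocol already ranks the two rules.

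**What to change.** 1. **Adverse Event Criteria and Reporting Procedures.** Add that the dose is not increased back while bleeding continues, or while active coagulopathy, hemodynamic instability or any contraindication in Risks and Discomforts is present, even if the event is judged unrelated. State that other unrelated events may be reversed at once.
2. **Dose Modification.** Move the bleeding rule here and grade it. Reduce the dose, by a stated amount, for mild bleeding. Hold until resolved for moderate or severe bleeding, or bleeding that needs clotting factor replacement, whatever the cause and for inpatients and outpatients alike. Let the Table 3 footnote refer to this section.
3. **Duration of Therapy (minor).** For restart after seven days, name the exclusion criteria alongside the inclusion criteria.

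The cost is a few sentences of protocol wording, plus occasional longer holds or a period of reduced lipid intake while a child is bleeding. Limiting the bar on reversal to bleeding and the listed conditions avoids needless under-dosing after other unrelated events.
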